#### Secondary Objectives

[figure not shown]
1. To evaluate how Glucagon RTU (Glucagon Injection) contributes to prevention of hypoglycemia during exercise and post exercise recovery.
2. To evaluate the effect of Glucagon RTU (Glucagon Injection) on insulin utilization during exercise.
3. To evaluate the effect of Glucagon RTU (Glucagon Injection) on PROs: Barriers to Physical Activity in Diabetes (Type 1) (BAPAD-1), Hypoglycemia Fear Survey (HFS-II), and Hypoglycemic Confidence Scale (HCS) after 12 weeks of outpatient exercise.

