#### Secondary Endpoints:

1. Interstitial glucose (IG) levels below target range, measured by unblinded CGM (inpatient and outpatient), defined as both time (in minutes) and mean decremental area over the curve (AOC (0-300 min) in minutes\*mg/dL) during exercise:
  - Below range, as defined by  $IG \leq 70 \text{ mg/dL} (\leq 3.89 \text{ mmol/L})$

- Below range, as defined by IG between 54 to 70 mg/dL (3–3.89 mmol/L)
- Below range, as defined by IG < 54 mg/dL (<3 mmol/L)
- Proportional time (percentage time within hypoglycemia IG  $\leq$  70 mg/dL (3.89 mmol/L) and clinically significant hypoglycemia IG < 54 mg/dL (3mmol/L)).

2. Insulin utilization as reported by subject at baseline, and weeks 4, 8 and 12 in the outpatient setting.
3. Change from Baseline to the end of the Outpatient Phase in PROs: Barriers to Physical Activity in Diabetes (Type 1) (BAPAD-1), Hypoglycemia Fear Survey (HFS-II), and Hypoglycemic Confidence Scale (HCS).

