**Other Secondary Endpoints:**

Change from Baseline in insulin utilization as reported by the subject at Weeks 4, 8, and 12 in the Outpatient Phase.

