**Exploratory Endpoints:**

1. Mean time and mean proportional time (%) within range, as defined by IG between 70 and 180 mg/dL (3.89 to 10 mmol/L) (CGM, 0 to 300 minutes with exercise), across the 2 CRC treatment arms.
2. Time, proportional time (percentage), and mean incremental Area Under Curve, plasma glucose  $>$  180 mg/dL (10 mmol/L), and (AUC (0-300 min) in minutes\*mg/dL) during exercise, across the 2 CRC treatment arms and the 3 outpatient treatment arms.
3. The time, proportional time (percentage), and mean incremental area under the curve (AUC) during which plasma glucose  $>$ 250 mg/dL (AUC (0-300 min) in minutes\*mg/dL) during exercise, across the 2 CRC treatment arms and the 3 outpatient treatment arms.
4. Incidence of overnight hypoglycemia as measured by CGM, across the 2 CRC treatment arms and the 3 outpatient treatment arms.
5. Compare the glucose tablet utilization during exercise, across the 2 CRC treatment arms and the 3 outpatient treatment arms.

6. Compare food (carbohydrate) intake pre/post exercise, across the 3 outpatient treatment arms.
7. Compare number of exercise sessions performed across the 3 outpatient treatment arms.
  - a. Conduct subgroup analysis for:
    - i. comparison of the number of qualified exercise sessions out of total number of exercise sessions conducted
    - ii. comparison of the number of qualified sessions meeting less than 30% proportional time at target HR
    - iii. comparison of the number of qualified sessions meeting greater than or equal to 30% proportional time at target HR
8. Compare number of minutes of exercise performed per week, across the 3 outpatient treatment arms.
9. Compare caloric expenditure during exercise, across 3 treatment arms.
10. The change from Baseline to end of study in body weight will be measured and analyzed across the 3 treatment arms.
11. Compare number of steps taken, and the distance achieved during exercise sessions across the 3 outpatient treatments arms.
12. The following assessments during exercise sessions will be captured from the wearable activity monitor: heart rate, daily steps, calories burned, distance covered, floors climbed, active minutes.
13. Change from baseline in HbA1c.

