#### **4.3.7 Secondary Endpoint Analysis:**

Glucose levels below target range will be measured and analyzed as the mean decremental area over the curve (AOC(0-5hrs) in minutes\*mg/dL) during exercise. AOC will be estimated using Trapezoidal Rule.

Analysis will be conducted for glucose levels below range (interstitial glucose  $\leq 70$  mg/dL (3.89 mmol/L), interstitial glucose between 54-70 mg/dL (3 – 3.89 mmol/L),  $<54$  mg/dL (3 mmol/L)) using a contingency table and treatment difference will be calculated using Chi square/Fisher's exact test.

Proportional time (percentage within serious hypoglycemia <54 mg/dL (3 mmol/L)) will be calculated and treatment difference will be calculated using ANOVA/Kruskal–Wallis test, based on whether the data is normally distributed or not respectively.

Insulin utilization as reported by subjects in Outpatient phase and change from baseline will be analyzed using ANOVA.

The Questionnaires will be analyzed using T Test/ANOVA for CRC/outpatient phase. For ANOVA, significant value will lead to a post hoc analysis for identifying the treatment pairs which are significantly different.

Changes from baseline in questionnaire values (numeric) will be analyzed by the ANCOVA model using treatment arm at Outpatient phase, treatment sequence in CRC phase, sex as factors with age, weight and baseline value as covariates.

Example of SAS syntax code that can be used for secondary endpoint analysis is provided in APPENDICES 2.

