#### **4.3.8 Exploratory Analysis:**

Glucose levels within range, >180 mg/dl, >250 mg/dl will be measured and analyzed as the mean incremental area under the curve (AUC(0-5hrs) in minutes\*mg/dL) during exercise.

Time and Proportional time (percentage within range, >180 mg/dl, >250 mg/dl) will be calculated and treatment difference will be calculated using ANOVA/Kruskal–Wallis test, based on whether the data is normally distributed or not respectively.

Generally, unless otherwise stated, the mean incidence rates will be compared using the T tests/ ANOVA or ANCOVA models using treatment arm at Outpatient phase, treatment sequence, obtained by combining the received treatments at CRC and Outpatient phase, sex as factors with, if applicable, age and weight as covariates.

Glucose tablet utilization during exercise, food (carbohydrate) intake pre/post exercise, number of exercise sessions completed across the 3 outpatient treatment arms , number of minutes exercised per week, number of calories burned per exercise sessions, number of steps, distance

covered, heart rate, floors climbed and change from Baseline in body weight will be compared for the treatment arms using T tests/ ANOVA at CRC/ Outpatient phase.

Incidence of overnight hypoglycemia will be compared for the treatment arms using Chi-Square/Fisher's exact tests at CRC/ Outpatient phase.

HbA1c data will be summarized using descriptive statistics (n, mean, SD, median, min, and max) for each scheduled study assessment, as well as change from baseline, will be summarized using ITT and PP Population.

Example of SAS syntax code that can be used for exploratory analysis is provided in APPENDIX 3.

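### Outpatient insulin utilization is tested by ANOVA with no baseline covariate and no model joining Weeks 4, 8 and 12, although baseline is collected and the questionnaire changes are baseline-adjusted

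*SAP*

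**What the plan says.** SAP section 3 lists insulin utilization twice. As a secondary endpoint it is "Insulin utilization as reported by subject at baseline, and weeks 4, 8 and 12 in the outpatient setting". As an other secondary endpoint it is "Change from Baseline in insulin utilization as reported by the subject at Weeks 4, 8, and 12 in the Outpatient Phase". The baseline value is therefore part of the planned data.

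For both forms SAP 4.3.7 gives one sentence of method: "Insulin utilization as reported by subjects in Outpatient phase and change from baseline will be analyzed using ANOVA". It names no covariate and does not say how the three weeks are combined or which of them is the main one. Protocol 12.4.3 names no method for insulin, so this sentence is the whole specification.

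SAP 2.4 defines change as the post-baseline value minus the baseline value. Later in SAP 4.3.7, changes in questionnaire values get an ANCOVA with arm, CRC sequence and "sex as factors with age, weight and baseline value as covariates".

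**The concern.** Insulin use is measured on the same people before and during outpatient treatment, so the baseline value is the natural covariate. The plan uses that covariate for the questionnaire changes but not for insulin.

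Two things follow.

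- **Precision.** The level analysis leaves all between-subject variation in the error term. The change analysis removes it by forcing a slope of 1 on baseline rather than estimating the slope.
- **Chance imbalance.** In small arms, baseline means will often differ. The level analysis carries part of that difference forward with the same sign, and the change analysis carries part of it with the opposite sign. The two planned analyses can then point in different directions, and the plan does not say which is definitive. With baseline as a covariate, level and change give the same treatment contrast.

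Without a joint model, the weeks are also left as separate looks. SAP 2.2 rules out imputation, so an ANOVA at one week drops anyone missing that week.

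**Working it through.** **Arm size.** The 14 per arm comes from SAP 1.3 and was set for the primary endpoint, not for insulin.

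- Effect size: 59/15² = 59/225 = 0.262, as stated.
- One-way ANOVA with three arms, alpha 0.05, noncentrality 3n × 0.262: power is 78.9% at n = 13 and 82.3% at n = 14. The stated 14 per arm is reproduced.
- 48 randomized with 15% attrition: 48 × 0.85 = 40.8 evaluable, or 13.6 per arm. About 14 per arm is a fair working figure.

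**Precision.** Let r be the correlation between baseline and follow-up insulin use. The documents do not give r, so it is an assumption shown over a range. With equal variances at baseline and follow-up, the residual variance relative to the follow-up variance is:

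- level only: 1
- change: 2(1 − r)
- ANCOVA with baseline: 1 − r²

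The ratios to ANCOVA are therefore 1/(1 − r²) for the level and 2(1 − r)/(1 − r²) = 2/(1 + r) for change.

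| r (assumed) | Level ÷ ANCOVA | Change ÷ ANCOVA |
|---|---|---|
| 0.5 | 1/0.75 = 1.33 | 2/1.5 = 1.33 |
| 0.8 | 1/0.36 = 2.78 | 2/1.8 = 1.11 |
| 0.9 | 1/0.19 = 5.26 | 2/1.9 = 1.05 |

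Estimating one slope at 14 per arm multiplies the ANCOVA variance by about 1 + 1/37 = 1.027. After that cost the level ratios are 1.30, 2.70 and 5.12, and the change ratios are 1.30, 1.08 and 1.02.

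In terms of power: an effect with 80% power under the three-arm F test on change at 14 per arm would have 90%, 84% or 82% under ANCOVA at r = 0.5, 0.8 or 0.9.

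**Chance imbalance.** In baseline SD units, the difference between two arm means has standard deviation √(2/14) = 0.38. A given pair differs by more than 0.5 SD with probability 19%. At least one of the three pairs does so with probability 38% (simulation with normal data).

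A baseline difference of 0.5 SD carries into the result as r × 0.5 for the level and (r − 1) × 0.5 for change:

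| r (assumed) | Level | Change | ANCOVA |
|---|---|---|---|
| 0.5 | +0.25 SD | −0.25 SD | about 0 in expectation |
| 0.8 | +0.40 SD | −0.10 SD | about 0 in expectation |
| 0.9 | +0.45 SD | −0.05 SD | about 0 in expectation |

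**The case against.** The case for leaving the sentence alone has real parts.

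- **Validity.** Randomization makes both ANOVAs unbiased on average, and omitting baseline does not inflate the type I error. This stands. The point concerns efficiency and conditional imbalance in an endpoint that the study was not sized for.
- **Baseline is already used for change.** This also stands. A reader might infer that the collected baseline is ignored altogether. That is true only of the level analysis. For change, what is missing is the covariate, and the loss is small if r is high.
- **Consistency with the questionnaires.** SAP 4.3.7 also gives the questionnaires a t test or ANOVA, and applies the ANCOVA only to their changes. The mismatch with insulin is therefore in the change analyses, where the covariate adds least at high r. The level analysis should be improved on its own merits.

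Stronger readings are tempting, but the documents do not support them.

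- **Body weight.** SAP 4.3.8 says that "change from Baseline in body weight will be compared for the treatment arms using T tests/ ANOVA", with no covariate, so a reader might extend the point to it. Weight is exploratory and analysed only as change. If its correlation is 0.95 or more (assumed), the variance saved is at most 1 − (1 + 0.95)/2 = 2.5%, about nil after the cost of the slope.
- **The assigned basal rule.** The objective in SAP 1.1 reads "To evaluate the effect of Glucagon RTU (Glucagon Injection) on insulin utilization during exercise". Basal delivery during exercise is halved by assignment in two arms and unchanged in the third, so a reader might infer that the rule alone could produce a significant three-arm result. The endpoint, however, is not restricted to exercise. If it means overall use (assumed), 2 to 3 sessions of 30 to 75 minutes come to 1 to 3.75 of 168 weekly hours. Halving a flat basal rate over that time changes weekly basal delivery by 0.3% to 1.1%.
- **Larger variance ratios.** Comparing change at one week with a baseline-adjusted average over three weeks gives bigger ratios. That mixes the gain from averaging with the gain from adjustment and compares different estimands.

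**Conclusion.** The point holds for insulin utilization as a matter of precision and chance imbalance, not of validity. For the level analysis the loss can be large: 1.33 to 5.26 times the ANCOVA variance for r between 0.5 and 0.9. For change it is modest: 1.33 down to 1.05 times. These figures assume equal variances at baseline and follow-up and a correlation that the documents do not report. The lack of a main week or contrast, and of a rule for when level and change disagree, adds to the case whatever the value of r.

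The conclusion does not extend to body weight. It does not say that the basal assignment would by itself generate a result. The objective is worded differently in the protocol synopsis (over 12 weeks of outpatient exercise) and in Protocol 5.1.2 and SAP 1.1 (during exercise). That difference needs reconciling as a separate matter.

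**What to change.** Replace the insulin sentence in SAP 4.3.7 with one repeated-measures model for Weeks 4, 8 and 12, with arm, week, arm-by-week and the baseline value as terms and a stated within-subject covariance. Name one main contrast in advance: which week, or the average over weeks, and which arms. A likelihood-based model also keeps any subject with at least one post-baseline week, without imputation.

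If a simpler analysis is preferred, use ANCOVA with baseline at each week and name the main week. Either way, a separate test of change becomes unnecessary.

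The example ANCOVA code in SAP Appendix 3 has no baseline term, so it needs one if it is reused here.

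The cost is one SAP paragraph and about one degree of freedom for the slope. No new data are needed.

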5.2.2. Key Secondary Endpoints

- Glucose levels below target range, measured by unblinded CGM (inpatient and outpatient), defined as both time (in minutes) and mean decremental area over the curve (AUC(0-300 min) in minutes*mg/dL) during exercise:
 - • Below range, as defined by interstitial glucose (IG) \leq 70 mg/dL (\leq 3.89 mmol/L)
 - • Below range, as defined by IG between 54 to 70 mg/dL (3 – 3.89 mmol/L)
 - • Below range, as defined by IG $<$ 54 mg/dL ($<$ 3 mmol/L)
 - • Proportional time (percentage time within hypoglycemia IG \leq 70 mg/dL (3.89 mmol/L) and clinically significant hypoglycemia IG $<$ 54 mg/dL (3 3 mmol/L))
- Insulin utilization as reported by the subject at Baseline, Weeks 4, 8, and 12 in the Outpatient Phase.
- Change from Baseline to the end of the Outpatient Phase in PROs: Barriers to Physical Activity in Diabetes (Type 1) (BAPAD-1), Hypoglycemia Fear Survey (HFS-II), and Hypoglycemic Confidence Scale (HCS),

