#### **4.3.6 Primary Endpoint Analysis:**

The primary efficacy hypothesis test for the study is as follows:

Null Hypothesis: There is no difference between the treatment groups in the mean incidence of hypoglycemia (glucose  $\leq 70$  mg/dL (3.89 mmol/L)) associated with an exercise session occurring within the 12 weeks of out-patient treatment as measured by BGM.

Alternative Hypothesis: There is a difference between treatment groups in the mean incidence of hypoglycemia (glucose  $\leq 70$  mg/dL (3.89 mmol/L)) associated with an exercise session occurring within the 12 weeks of out-patient treatment as measured by BGM.

Incidence rate per subject is calculated by summing the number of exercise sessions completed within 12 weeks and dividing this denominator by the number of hypoglycemic events that

occurred during those exercise sessions (Incidence Rate = number of exercise sessions / inter/post-exercise hypoglycemic events). Events associated with an exercise session are defined as hypoglycemic events that occur during or within 30 minutes of exercise completion.

The primary efficacy analysis will be analyzed by ANOVA comparing the mean incidence rate between the three treatment groups. All statistical significance testing will be two-sided with a p-value  $<0.05$ . Efficacy endpoints will be analyzed using the ITT and PP analysis populations for Outpatient phase, if performed F-test yields an overall p-value less than 0.05 ( $p<0.05$ ), post-hoc analysis of groups means will be conducted to statistically determine which group means differ.

Parameters that do not meet normality criterion will be analyzed non-parametrically. Overall treatment effect will be assessed using Friedman's test. If the overall treatment effect is significant in the Friedman's test, pairwise treatment comparisons will be assessed using the following tests.

- If the difference between two treatments is normally distributed (i.e., the p-value is  $\geq 0.05$  for Shapiro-Wilk test, the Tukey Test will be used.
- If the difference between two treatments is not normally distributed and the distribution is highly skewed, then the sign test/Kruskal Wallis test will be used.

Example of SAS syntax code that can be used for primary endpoint analysis is provided in APPENDIX 1.

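### SAP 4.3.7 gives BAPAD-1, HFS-II and HCS both an unadjusted ANOVA and a baseline-adjusted ANCOVA, never says which decides, and attaches the pairwise step only to the ANOVA

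*SAP*

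**What the plan says.** SAP section 3 defines one endpoint per questionnaire: "Change from Baseline to the end of the Outpatient Phase in PROs". The protocol lists it under "5.2.2. Key Secondary Endpoints"; the SAP heading says only secondary. Protocol 12.4.3 names no test for it.

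SAP 4.3.7 gives two instructions in consecutive paragraphs:

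- "The Questionnaires will be analyzed using T Test/ANOVA for CRC/outpatient phase". The variable (score or change) is not stated. If the ANOVA is significant, pairwise comparisons between arms follow, by a method the section does not name.
- The next paragraph adds a second model: "Changes from baseline in questionnaire values (numeric) will be analyzed by the ANCOVA model using treatment arm at Outpatient phase", with CRC treatment sequence as a further factor and "sex as factors with age, weight and baseline value as covariates".

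Neither is called primary, supportive or a sensitivity analysis. SAP 4.3.6 adds "All statistical significance testing will be two-sided with a p-value" threshold of 0.05. That sentence sits in the primary-endpoint section but is worded for all testing, and no alpha is split for the questionnaires. SAP 5.1 lists descriptive score tables (14.2.2.2 to 14.2.2.4) and, per questionnaire and population, one table of the analysis of change from baseline (14.2.4.2 to 14.2.4.4). The titles of the latter do not name the method.

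**The concern.** Followed as written, the SAP produces two between-arm p-values for each questionnaire, on the same subjects and the same question. The two can differ. A chance baseline imbalance stays in a one-way ANOVA but is adjusted for in the ANCOVA, so an arm difference may be significant in one and not in the other. With no ranking, the choice could be made after the results are seen.

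The pairwise step makes this worse. The objectives compare glucagon with and without basal reduction against basal reduction alone, so pairwise results are what a reader wants. The only pairwise instruction follows the ANOVA. A programmer could reasonably report the overall p-value from the adjusted model and the pairwise claims from the unadjusted one.

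**Working it through.** **1. Group size.** SAP 1.3 gives variance of means 59, SD 15, power 80% and alpha 0.05. Then f² = 59/15² = 0.262 and, at 14 per arm, λ = 42 × 0.262 = 11.0. The noncentral F gives power 82.3% at 14 per arm and 78.9% at 13, so the plan's 14 is reproduced. This sizing is for the primary endpoint; no figure is given for the questionnaires. I use 14 per arm as the evaluable number.

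**2. Models compared.** Baseline and follow-up are simulated as bivariate normal, SD 1, correlation ρ. The documents do not give ρ, so it is varied. In each simulated trial the arm effect is tested by F = [(RSS₀ − RSS₁)/2] / [RSS₁/df].

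- ANOVA: arm only, df = 42 − 3 = 39. It is run on change and on final score, because the SAP does not say which.
- ANCOVA of change: intercept, baseline, sequence, sex, age, weight and two arm terms, df = 42 − 8 = 34. Sequence, sex, age and weight are assumed unrelated to outcome.

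**3. No true effect, 14 per arm, 20,000 trials per row, each test at 0.05.**

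| ρ | ANCOVA alone | Either significant, ANOVA on change | Either significant, ANOVA on final score | Tests disagree (change / final) |
|---|---|---|---|---|
| 0.3 | 4.5% | 7.7% | 6.7% | 5.9% / 4.0% |
| 0.5 | 5.0% | 7.6% | 7.7% | 5.5% / 5.4% |
| 0.7 | 4.8% | 7.3% | 8.3% | 4.8% / 6.8% |
| 0.9 | 5.2% | 7.2% | 9.6% | 4.2% / 8.9% |

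The simulation standard error near 5% is √(0.05 × 0.95/20,000) = 0.15 points. Across separate runs with ρ from 0.3 to 0.8, the either-test rate is about 6.5–9%. At 16 per arm (48/3) it is 6.7–9.2% for ρ from 0.3 to 0.9. For scale, two independent tests would give 1 − 0.95² = 9.75%.

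**4. An assumed effect.** One arm shifted by 1 SD, ρ = 0.5, 14 per arm. The variance of change is 2(1 − 0.5) = 1, the same as for the final score, so both forms of ANOVA have the same power, about 75%. Adjusting for baseline leaves variance 1 − 0.5² = 0.75. ANCOVA power is about 86% with baseline as the only covariate and about 81% with the SAP's full covariate list. The ANOVA and ANCOVA verdicts differ in about 15% of trials. With 0.8 SD in both glucagon arms and ρ from 0.3 to 0.7, they differ in 13–25% (ANOVA on change) or 16–32% (on final score).

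**5. Three questionnaires.** If independent, one test each gives 1 − 0.95³ = 14.3%. Either test at 7.63% each (ρ = 0.5, ANOVA on change) gives 1 − (1 − 0.0763)³ = 21.2%. With an assumed correlation of 0.5 between questionnaires, the figures are 13% with the ANCOVA alone (baseline covariate only) and 17–20% with both tests. The second test therefore adds 4 to 7 points (17 − 13 and 20 − 13).

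**The case against.** The best reply is that the ANCOVA is already the intended analysis. The endpoint is change from baseline, and in 4.3.7 only the ANCOVA sentence names change for the questionnaires. The preceding sentence, on insulin utilization, mentions change explicitly when change is to go into an ANOVA. The table list has one inferential table of change per questionnaire and population, and no table of an ANOVA on scores. The ANOVA sentence also looks generic: it pairs a t test with the CRC phase, yet these three questionnaires are completed only at Visit 3, before dosing, and at Visit 11, so they offer no CRC treatment comparison.

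This stands as a strong hint, and a reader who inferred that the SAP gives no indication at all would go too far. It is still not a specification. No sentence ranks the tests, the table titles name no method, and the pairwise step belongs to the ANOVA alone. The only ANCOVA code (Appendix 3) is labelled exploratory, has no baseline term and uses a lower one-sided 0.025 limit, so it does not implement the 4.3.7 model.

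Three further limits also stand. The study is a Phase 2 trial of preliminary efficacy. It claims no familywise control for secondary endpoints, and protocol 12.4.3 says its named t tests are uncorrected. The disagreement rate under an effect depends on the effect and correlation assumed.

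**Conclusion.** The point holds as an unresolved choice of analysis for three secondary endpoints; the primary endpoint is untouched. Its size is moderate: about 6.5–9% false positives per questionnaire instead of 5% if either test may count, and conflicting verdicts in about 15% of trials under an assumed 1-SD effect in one arm at correlation 0.5. These figures rest on 14 per arm, normal scores, assumed correlations and, where the full ANCOVA is used, covariates unrelated to outcome.

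Three stronger readings are tempting but unsupported:

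- That the error rate doubles. The two tests share data and are correlated, so the rise stops short of 10%.
- That the duplicate test causes the 17–20% across three questionnaires. Most of it, 13%, arises from three unadjusted endpoints with one test each.
- That the ANCOVA gains 11 points of power (86 against 75). With the SAP's own covariates the gain is about 6 (81 against 75).

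The change should be made before unblinding, mainly so that the deciding test and the source of pairwise claims are fixed in advance.

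**What to change.** In SAP 4.3.7:

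- State that the ANCOVA of change from baseline, with the factors and covariates already listed, is the single deciding between-arm analysis of BAPAD-1, HFS-II and HCS.
- Take pairwise arm differences and 95% CIs from that model, reported in Tables 14.2.4.2 to 14.2.4.4.
- Drop the outpatient ANOVA and its post-hoc step for these questionnaires, or label both supportive.
- Keep raw scores descriptive in Tables 14.2.2.2 to 14.2.2.4.

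The appendix code for this analysis should match the named model, including the baseline term and two-sided limits. The cost is a short text edit and no change to data collection. No table is saved, because no ANOVA-only table is listed. With one deciding test, the simulated error per questionnaire returns to about 5%. Testing three questionnaires in two populations without adjustment is a separate matter that this edit does not settle.
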